## Study Population:

- Total of 39 terminal-stage cancer patients receiving palliative care
- Intervention group (n = 22), Control group (n = 17)

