### **Primary Outcomes:**

1. Pain level (measured by Visual Analog Scale - VAS)
2. Dyspnea (measured by Cancer Dyspnea Scale - CDS)
3. Functionality (measured by ESAS-r functional subscale)

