### **Secondary Outcomes:**

- SpO2, pulse rate, hemoglobin, leukocyte, platelet, CRP levels

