## **Data Analysis:**

- Data analyzed using SPSS Statistics v27
- Kolmogorov-Smirnov test for normality
- t-tests, Wilcoxon signed-rank test, and Mann-Whitney U test as appropriate
- Effect size reported using Cohen's d

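### Cohen's d is the only planned effect measure, with no definition, no difference in scale points and no confidence interval, and it may not match outcomes tested by Mann-Whitney

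*Combined protocol and SAP*

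**What the plan says.** The analysis plan is the short list under Data Analysis. After the software it names a pre-test, "Kolmogorov-Smirnov test for normality", then the tests, "t-tests, Wilcoxon signed-rank test, and Mann-Whitney U test as appropriate", and then the effect measure, "Effect size reported using Cohen's d". No other section adds to this.

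The list mixes a paired rank test (Wilcoxon signed-rank) with a between-arm rank test (Mann-Whitney). The effect-size line does not say which comparison d describes, whether it is computed on Day 5 values or on changes from Day 0, or whether it is confined to outcomes analysed by t-test.

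The three primary outcomes are scale scores: pain on a VAS, dyspnea on the CDS, and function on an ESAS-r subscale. The secondary outcomes are "SpO2, pulse rate, hemoglobin, leukocyte, platelet, CRP levels". Study Population gives 22 intervention and 17 control patients, 39 in all. The document states no alpha, confidence level, expected effect or SD.

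**The concern.** Cohen's d is a difference in means divided by an SD. Three things follow from making it the only effect measure.

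- **No clinical size.** A reader needs to know how many points of pain, dyspnea or function separate the arms. Without the SD, d cannot be turned back into points.
- **No uncertainty.** With 39 patients any d is imprecise. A bare value of 0.5 can be read as a medium effect, or dismissed as no effect if its p-value is above 0.05. The data would support neither reading.
- **Possible mismatch with the test.** If the normality test sends an outcome to Mann-Whitney, the p-value comes from ranks while d comes from means and SDs. A few extreme values can inflate the SD and shrink d while hardly moving the ranks, so the two numbers side by side can point to different conclusions.

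The first two apply to every outcome, whatever its distribution. The third depends on the data.

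**Working it through.** The plan states no figure that could be reproduced. The checks below use its arm sizes (22 and 17, Study Population). Two-sided alpha 0.05 and 95% confidence are assumed.

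**1. Precision of d**

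SE(d) = √[(n₁ + n₂)/(n₁n₂) + d²/(2(n₁ + n₂))] = √[39/(22 × 17) + d²/78]

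| d | SE | 1.96 × SE | 95% CI |
|---|---|---|---|
| 0 | 0.323 | 0.633 | -0.63 to 0.63 |
| 0.5 | 0.328 | 0.643 | -0.14 to 1.14 |
| 0.8 | 0.335 | 0.657 | 0.14 to 1.46 |

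Exact intervals from the noncentral t with 37 degrees of freedom agree: -0.15 to 1.14 at d = 0.5, and 0.14 to 1.45 at d = 0.8.

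**2. What d hides in scale points**

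Difference = d × SD. No SD is given, so take 1, 2 or 3 points as a range. Then d = 0.5 is 0.5, 1.0 or 1.5 points, with 95% CIs of -0.15 to 1.14, -0.29 to 2.28 and -0.44 to 3.42.

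**3. Why the type of d must be stated**

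If d were computed on paired changes with the SD of change, then for the same mean change and equal SDs at both times it would equal the between-person d multiplied by 1/√(2(1 - r)), where r is the Day 0 to Day 5 correlation. With r assumed to be 0.7 this is 1/√0.6 = 1.29; with r = 0.8 it is 1/√0.4 = 1.58. The same label could thus carry values 29% or 58% apart.

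**4. Agreement between d and Mann-Whitney**

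Simulated trials of 22 and 17 patients, 20,000 per setting, lognormal data, true geometric mean ratio 0.5. The lognormal shape and log-SDs are assumptions meant to resemble CRP. Results among trials with Mann-Whitney p < 0.05:

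| Assumed log-SD | 95% CI of d includes zero | d has the opposite sign to the ranks |
|---|---|---|
| 1.0 | about 28% | 0.3% |
| 1.5 | about 55% | 2.7% |

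A second set of 10,000 runs per setting used true shifts of 0.5 to 0.8 log-SD. Among significant Mann-Whitney results, d was non-significant in 35-45% (log-SD 1.0) and 62-68% (log-SD 1.5), and the sign was reversed in 0.2-1.8%. With normal data and a true d of 0.8, d was non-significant in only about 3%, with no reversals.

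**5. The mechanism on a bounded scale**

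This is a constructed 0-10 example, not a prediction. Intervention: six patients at 1, seven at 2, five at 3, and one each at 8 and 9 with two at 10. Control: five at 3, eight at 4, four at 5. The medians are 2 and 4 and Mann-Whitney p = 0.002. The means are 3.27 and 3.94, d = -0.29, and its 95% CI is -0.92 to 0.35.

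**The case against.** The strongest reply is that the plan does not commit to misusing d. Rank tests are to be used only where appropriate, after a normality check, so none may be needed. The effect-size line does not say that d will accompany a rank test or a within-arm comparison. That is right. A reader might infer that d is planned for every outcome and for both paired and between-arm comparisons, but the document states neither. What stands is that the scope and type of d are undefined and that nothing excludes those uses. The ratios in step 3 illustrate that ambiguity, not a stated intention.

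A reader might also infer that d will often point in the opposite direction to its own p-value. The calculations do not support that. Counting reversals over all simulated trials gives a larger share, but nearly all of them occur where Mann-Whitney is not significant and both estimates lie close to zero, which contradicts no p-value. Among significant results reversal is rare.

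Third, an interval for d that includes zero beside a significant rank test is not strictly a contradiction. It partly reflects the lower power of mean-based methods on skewed data. This stands too, and mismatch is the better word. The simulated figures also describe an assumed laboratory marker, one of six secondary outcomes. They should not be carried over to the VAS, CDS or ESAS-r, for which no distributions are given.

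None of this touches the missing scale-point difference or the missing interval.

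**Conclusion.** The point holds in a limited form. The plan offers Cohen's d alone, undefined as to comparison and not tied to the t-test, with no difference in original units and no confidence interval. The loss of information affects all outcomes, including the three primary ones, and needs no distributional assumption: at these arm sizes the uncertainty is about ± 0.64 around any moderate d.

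The mismatch with Mann-Whitney is conditional. It requires that an outcome be sent to a rank test, and its size rests on assumed skewness: about 28-55% of significant rank results under lognormal data with log-SD 1.0 to 1.5, and about 3% for normal data.

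The hypothesis tests and their error rates are unaffected. The matter is one of interpretation and should be corrected, but it does not invalidate the trial.

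**What to change.** Replace the effect-size line with:

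> The effect measure for each outcome is the between-arm difference with 95% CI in the original units: the mean difference where a t-test is used, and the Hodges-Lehmann difference where Mann-Whitney is used. A between-arm standardised effect with 95% CI is supplementary and given only for outcomes tested by t-test.

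The text should also name the quantity compared (Day 5 value or change from Day 0), and it should be the same for the test and the estimate. A log-scale analysis with geometric mean ratios need not be made compulsory for the laboratory values: the document gives no evidence on their distributions, and a second estimate beside the Hodges-Lehmann difference would reopen the question of which one belongs to the test.

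The cost is a change of wording and slightly more analysis work, with no new patients or data. Results will look less certain because the intervals are shown. As the stated completion date is May 2025, the change may be made after data collection; if so, it should carry its date and be reported as such.

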## **Ethical Considerations:**

- Study approved by local ethics committee (IRB)

-Informed consent was obtained from all participants or their legal representatives.

-University Ethics Committee was approved this study (# 44948; July 4, 2024).

## **Study Timeline:**

- Start Date: October 2024
- Completion Date: May 2025
